Appendix 12 Protocol Amendment History

The information for the current amendment is on the title page.

2.0	13NOV2024	PPD	Section 5: Updated the table column "IAP section"  Section 10.1: Re-ordered the ineligible and eligible subjects in the disposition table to align with the TLFs. Section 10.2.1: Removed the summary presentation for PDs attributable to the COVID-19 pandemic. Section 11.1: Updated the age categories and split ethnicity in 2 separate lines.  Section 15.2.1: Added the additional analysis information for the presentation of TEAEs during the Rollover study. Section 15.2: Clarified the content of the overall summary of AEs table and tables of TEAEs by SOC and PT. Section 15.3.2: Added that SAEs will be presented for events that occurred during the on-treatment period as well as for events that occurred during the Rollover study to align with the new TLFs that were added. Section 15.3.3: Added details for the AESIs presentation Section 15.4: Added more details for the listings content Section 18.1: removed the details for the AESIs presentation, which were moved to Section 15.3.3.

4

Purpose of the Integrated Analysis Plan

The purpose of this IAP is to document technical and detailed specifications for the final analysis of data collected for Study MS200647-0054. Results of the analyses described in this IAP will be included in the CSR. Additionally, the planned analyses identified in this IAP may be included in regulatory submissions or future manuscripts. Any post-hoc, or unplanned analyses performed to provide results for inclusion in the CSR but not identified in this prospective IAP will be clearly identified in the CSR.

The IAP is based upon Section 9 (Statistical considerations) of the study protocol and protocol amendments and is prepared in compliance with ICH E9. It describes analyses planned in the protocol and protocol amendments.

The wording used in this IAP is chosen to best match the respective wording in the study protocol template, the Clinical Study Report (CSR) template, CDISC requirements and special requirements for table layouts. Therefore, the following approach is used:

Generally, the term ‘participant’ will be used instead of ‘subject’ or ‘patient’. However, in tables and listings the term ‘subject’ will be used to match CDISC requirements, except for in-text tables where ‘participant’ will be used to match the CSR and protocol templates. Similarly, the term ‘study intervention’ will be used in this document instead of ‘treatment’ to match protocol and CSR templates, however, tables and listings will use ‘treatment’ for brevity reasons. Exceptions from this rule are commonly used terms like “on-treatment”, “treatment-emergent”, “treatment policy”, “subject-years”, “by-subject”, or names of eCRF pages like “Treatment Termination” page.

5

Objectives and Endpoints

Objectives	Endpoints	IAP section
Primary		
To evaluate clinical safety of bintrafusp alfa in participants with solid tumors who continue treatment after completion of the primary/mainanalyses in parent bintrafusp alfa studies	Occurrence of AEs and treatment-related AEs, starting from baseline in parent study	15.1.1
Secondary		
To evaluate clinical efficacy of bintrafusp alfa based on OS	OS, starting from baseline in parent study	14.1.1

CCI

6 Overview of Planned Analyses

A final analysis will be performed. This IAP covers the final analyses for efficacy and safety. Statistical analyses will be performed using cleaned Rollover eCRF data as well as data from the respective parent studies needed for the analysis but not collected in the Rollover eCRF.

6.1 Final Analysis

All final, planned analyses identified in the Clinical Study Protocol and in this IAP will be performed only after the last participant has completed the period of the study with all study data in-house, all data queries resolved, and the database locked.

Subject survival follow-up will continue until up to a maximum of 5 years after the last participant receives the last dose of bintrafusp alfa. Therefore, the full database lock will take place either 5 years after the last subject receives the last dose of bintrafusp alfa or this duration may be shortened if the last patient was lost to follow-up or at the discretion of the Sponsor for any given indication. The Sponsor may terminate the study at any time once access to study intervention for participants still benefiting is provisioned via expanded access, marketed product, or another mechanism of access as appropriate.

A Data Review Meeting will be held prior to database lock. In addition, no database can be locked until this IAP has been approved.

7 Changes to the Planned Analyses in the Clinical Study Protocol

Subsections of COVID-19 impact on the study are added.

The final analysis will be performed after the last participant has completed the period of study, instead of 'the last participants is off treatment' as mentioned in the section 9.4.4 in the Clinical Study Protocol.

CCI

8 Analysis Sets and Subgroups

8.1 Definition of Analysis Sets

Enrolled Analysis Set

All subjects consented for the Rollover study.

Full Analysis Set (FAS)

The FAS will be defined as in the protocol of the parent study and include all participants who receive at least one dose of study intervention in the Rollover study.

Safety Analysis Set (SAF)

The SAF will be defined as in the protocol of the parent study and include all participants who receive at least one dose of study intervention in the Rollover study.

The final decision to exclude participants from any analysis set will be made during the Data Review Meeting prior to database lock.

Analyses per Analysis Set

The following table summarizes the use of the analysis sets in the different analyses.

Analyses	Analysis Set		
	Enrolled Analysis Set	Full Analysis Set	Safety Analysis Set
Disposition	✓		
Demographic and Baseline Assessments: Demographics, Medical History and Disease History		✓	
Previous and Concomitant Therapies		✓	
Compliance and Exposure			✓
Efficacy: Secondary Endpoint		✓	
Safety and Tolerability			✓

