10.1 Disposition of Participants and Discontinuations

The number and percentage of participants in each of the below disposition categories will be presented by total and per indication or per parent protocol of the corresponding parent study, where applicable. Percentages will be presented with respect to the number of consented participants in the Rollover study.

- Total number of participants consented (i.e. participants who gave informed consent)
- Number of ineligible subjects and reason for ineligibility (subject did not meet all eligibility criteria, withdrawal by-subject, PD, adverse event, lost to follow-up, death and other).
- Number of eligible subjects

- Number of participants who enrolled before Start of COVID-19 pandemic.
- Number of participants who enrolled after Start of COVID-19 pandemic.
- Number of participants who terminated the study treatment by main reason (adverse event, lost to follow-up, protocol non-compliance, death, PD, withdrawal by subjects and other).
- Number of participants who terminated the study treatment due to COVID-19.
- Number of participants who discontinued the study and primary reasons for study discontinuation (adverse event, lost to follow-up, protocol non-compliance, death, withdrawal by participants and other).
- Number of participants who discontinued the study due to COVID-19.
- Number and percentage of participants who re-initiated the bintrafusp alfa treatment.
 - Number and percentage of subjects who discontinued treatment after re-initiation.

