The exposure duration (in weeks) of study intervention since first administration of study interventions in the parent study will be calculated based on the safety analysis set per indication or per parent protocol of the corresponding parent study. The detail on the calculation of exposure duration is described in Section 9.8.

14 Efficacy Analyses

The following analyses will be performed based on the FAS and presented as listings.

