14.1 Secondary Endpoints

14.1.1 Secondary Objective: Analysis of the secondary endpoints

The below analysis will be performed per indication or parent protocol of the corresponding parent study cohort if there are at least 5 subjects enrolled per indication or parent protocol of the corresponding parent study cohort. Listings of the time-to-events will be presented.

Analysis (AnalysisSet)	Derivation	Statistical Analysis Methods
Secondary endpoint: OS, starting from baseline in parent study.		
Secondary (FAS)	
OS time (in months) is defined as the date from baseline of parent study to the date of death due to any cause.
 
For participants alive at the time of data analysis or who are lost to follow-up, the OS will be censored at the date of data cut-off or date of last contact defined in Section 9.5.
 
OS (months) = (date of death/censoring – date of parent baseline + 1) / 30.4375
	
Date of death, with the reasons for censoring (alive, withdrawal of consent and lost to follow-up) will be presented in a participant listing.
 
OS will be estimated by the KM method. Median time to event will be reported, along with 25th and 75th percentiles.

The tumor evaluation data will be listed.

15 Safety Analyses

This section includes specifications for summarizing safety endpoints that are common across clinical studies such as adverse events, laboratory tests and vital signs.

Safety analyses will be done on the safety analysis set.

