All analyses described in Section 15.2 will be based on TEAEs if not otherwise specified. The AE listings will include all AEs (whether treatment-emergent or not). AEs outside the on-treatment period will be flagged in the listings.

In addition, selected analyses will be repeated for the TEAEs that occurred during the Rollover study. TEAEs occurring during the Rollover study are defined as TEAEs with onset or worsening (seriousness or severity) date after the first dose of study intervention in the Rollover study.

Unless otherwise specified, TEAEs will be summarized by number and percentage of participants with the TEAE by primary SOC and PT in the category of interest in alphabetical order, per indication or per parent protocol of the parent study.

Each participant will be counted only once within each SOC or PT. If a participant experiences more than one AE within a SOC or PT for the same summary period, only the AE with the strongest relationship or the worst severity, as appropriate, will be included in the summaries of relationship and severity.

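### If the FAS means Rollover-dosed participants only, as SAP 8.1 most likely intends, the Kaplan-Meier OS from parent baseline contains guaranteed survival time and needs a conditional label

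*SAP*

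**What the plan says.** Protocol 9.3 defines the FAS for each parent study as that study's protocol does. Protocol 9.4 bases endpoint analyses on those sets, merges parent and Rollover data, and keeps parent baseline as the baseline for safety and efficacy.

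SAP 8.1 repeats the reference to the parent protocol and adds that the FAS will "include all participants who receive at least one dose of study intervention in the Rollover study". The SAF has the same clause. The Enrolled Analysis Set is "All subjects consented for the Rollover study". The table in SAP 8.1 assigns the secondary efficacy endpoint to the FAS.

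SAP 14.1.1 states that "OS time (in months) is defined as the date from baseline of parent study to the date of death due to any cause", and that "OS will be estimated by the KM method. Median time to event will be reported, along with 25th and 75th percentiles". The analysis is run "if there are at least 5 subjects enrolled per indication or parent protocol" cohort. The opening of SAP Section 14, however, says the efficacy analyses are "performed based on the FAS and presented as listings".

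For safety, SAP 15.2 repeats selected tables for "TEAEs with onset or worsening (seriousness or severity) date after the first dose of study intervention in the Rollover study". OS has no visible counterpart. The visible part of SAP Section 7 does not list a change to the FAS.

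**The concern.** A participant must be alive to receive a Rollover dose. If that dose is the condition for being in the FAS, the interval from parent baseline to that dose carries no risk of death in this set, yet it counts in full towards OS. Kaplan-Meier with everyone at risk from parent baseline then gives a curve that stays at 1.0 until at least the earliest Rollover entry.

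OS is the only visible efficacy endpoint, and its stated objective is to evaluate clinical efficacy. SAP Section 4 foresees use in regulatory submissions or manuscripts. An unlabelled median on the parent study's time origin invites comparison with parent-study OS. Protocol 2.3 reports that three discontinued randomised studies showed poorer hazard ratios or a low likelihood of added benefit, so the two kinds of result could easily be set side by side.

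The SAF raises a related point. SAP 15.3.1 counts deaths within 60 days after first dose. If that is the first parent-study dose, the count is zero by construction for everyone who rolled over after day 60.

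**Working it through.** The plan states no expected OS, time to rollover or event count, so there is no figure of its own to reproduce.

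**Step 1: which FAS?** The sentence in SAP 8.1 can mean the parent FAS limited to Rollover-dosed participants, or the parent FAS with those participants among its members. The main support for the first is that a whole-parent FAS would be larger than the Enrolled Analysis Set, which holds only those who consented to Rollover. Two further points are weaker:

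- SAP 10.1 says "Percentages will be presented with respect to the number of consented participants in the Rollover study", but disposition uses the Enrolled set, so this says little about the FAS.
- A minimum of 5 suits a study expecting at least 10 participants (Protocol 1.1). Protocol 2.3 implies bintrafusp alfa arms of 16/0.106 = 151, 11/0.075 = 147 and 3/0.041 = 73, where the rule would never bind. But it is worded per parent study cohort, and Appendix 10 includes dose-escalation studies whose cohorts could be small.

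**Step 2: lower bound, free of distributional assumptions.** Write OS_i = e_i + p_i, where e_i is the time from parent baseline to first Rollover dose and p_i ≥ 0 is survival after it. Kaplan-Meier drops only at deaths, and each death time is ≥ e_i ≥ min(e). Every reported percentile is therefore ≥ min(e), with or without censoring.

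**Step 3: size with a fixed entry time L (assumed).** For exponential OS with median m, the quantile is q_p = −m·ln(1−p)/ln 2. Among those alive at L, the quantile from parent baseline is L + q_p, so the excess is L. With m = 12 the true quartiles are 5.0/12.0/24.0 months, and the estimates are:

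- L = 6: 11.0/18.0/30.0
- L = 12: 17.0/24.0/36.0
- L = 24: 29.0/36.0/48.0

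**Step 4: size with variable entry (assumed).** Simulation of 20,000 groups per cell: exponential OS, entry time drawn uniformly, only those alive at entry kept, no censoring, median taken as the first time the curve reaches 0.5. Typical parent-baseline median in months, n = 5 / n = 10:

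| True median | Entry 6–18 | Entry 6–30 | Entry 12–36 |
|---|---|---|---|
| 6 | 17.3 / 16.5 | 19.6 / 18.5 | 25.7 / 24.5 |
| 12 | 23.7 / 22.1 | 28.6 / 26.8 | 34.7 / 32.8 |
| 24 | 35.8 / 32.7 | 41.4 / 38.1 | 47.5 / 44.1 |

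The excess over the true median runs from 32.7 − 24 = 8.7 to 47.5 − 24 = 23.5 months. With entry at 1 to 6 months it is only about 0 to 4 months. In the tabulated windows, the median from first Rollover dose is 10.8 to 23.1 months lower than from parent baseline.

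**Step 5: reach.** With 10 participants at most 10/5 = 2 groups can qualify. If participants spread equally over the ten studies in Appendix 10, the chance that any study reaches 5 is about 2% at N = 10, 40% at N = 20 and 95% at N = 30. With an assumed uneven spread (Dirichlet, parameter 0.5) it is about 42% at N = 10 and 98% at N = 20.

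**The case against.** **The estimate is valid for its own set.** The SAP never says it estimates OS for the parent population. There is no comparator or test in the visible text, and OS is descriptive. This stands. A reader might infer that the Kaplan-Meier analysis is simply wrong; the documents do not support that. The fault is a missing label on a conditional quantity.

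**The restricted FAS is not certain.** This also stands. If the whole parent FAS is meant, the guaranteed time does not arise. SAP 8.1 would still need rewording.

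**Text is missing.** SAP Section 9 is redacted, including the 9.5 rules that 14.1.1 cites for last contact. Entry-time handling there cannot be excluded. Protocol 9.4 also allows separate plans or addenda for parent studies.

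**The months depend on chosen entry windows.** Correct. Protocol 2.3.2 says only that continuing participants had been treated for a prolonged period. A reader might take 9 to 24 months as the expected inflation; only the lower bound in step 2 is free of such assumptions.

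**Grouping by indication.** A reader might assume this makes groups of 5 more likely. The direction is undetermined: it merges some studies but splits the two Phase I studies that span several tumour types.

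**OS from first Rollover dose should not replace the endpoint.** Agreed. The protocol defines OS from parent baseline, and the alternative origin mixes continuing participants with those reinitiating after progression or an adverse event (Protocol 5.1).

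**Delayed-entry Kaplan-Meier is no easy remedy.** In assumed scenarios the curve fell to zero before the last death in 7 to 17% of samples at n = 5 and 3 to 8% at n = 10. It also leaves the selection on treatment status and response untouched.

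**Conclusion.** The point holds as one of clarification and labelling. SAP 8.1 most likely restricts the FAS to Rollover-dosed participants, which departs from Protocol 9.3 and 9.4. On that reading the OS percentiles in SAP 14.1.1 are conditional on reaching a Rollover dose and cannot be read as OS from parent baseline for parent-study participants. The upward direction relative to that population follows from step 2 for any percentile whose true value lies below the earliest entry; elsewhere it rests on the illustrative models. The size is unknown. The assumed ranges, about 0 to 4 months for entry at 1 to 6 months and about 9 to 24 months for entry at 6 to 36 months, rest on exponential survival, no censoring and no selection beyond being alive.

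The practical reach may be small, because few groups may have 5 participants. If the statement that efficacy is shown as listings governs, no median is reported at all. Confidence is moderate because of the ambiguous sentence and the redacted section.

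**What to change.** 1. In SAP 8.1, state whether the FAS is the parent-study FAS or only its Rollover-dosed members. Reconcile this with Protocol 9.3 and 9.4, and record any change in SAP Section 7 if the redacted text there does not already do so.
2. If it is Rollover-dosed only, keep the protocol-defined OS from parent baseline, but label the median and quartiles *conditional on receiving a Rollover dose; not comparable with parent-study OS*. Show each participant's time to first Rollover dose in the OS listing. Add Kaplan-Meier OS from first Rollover dose as a supplementary analysis, entered in SAP Section 7, with a note that this origin mixes continuing and reinitiating participants.
3. Reconcile the listings-only statement at the start of SAP Section 14 with the Kaplan-Meier estimates in 14.1.1.
4. In SAP 15.3.1, state whether first dose means the parent or the Rollover dose.

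The cost is SAP wording and light programming. The first Rollover dose date is already needed for the SAP 15.2 tables. The downside is a supplementary median that will look less favourable than the parent-baseline one.

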8.2 Subgroup Definition and Parameterization

No subgroup analyses will be performed in the study.

[figure not shown]
CCI

CCI

CCI

CCI

CCI

10 Study Participants

The subsections in this section include specifications for reporting participant disposition and study intervention/study discontinuations. Additionally, procedures for reporting protocol deviations are provided.

10.1 Disposition of Participants and Discontinuations

The number and percentage of participants in each of the below disposition categories will be presented by total and per indication or per parent protocol of the corresponding parent study, where applicable. Percentages will be presented with respect to the number of consented participants in the Rollover study.

- Total number of participants consented (i.e. participants who gave informed consent)
- Number of ineligible subjects and reason for ineligibility (subject did not meet all eligibility criteria, withdrawal by-subject, PD, adverse event, lost to follow-up, death and other).
- Number of eligible subjects

- Number of participants who enrolled before Start of COVID-19 pandemic.
- Number of participants who enrolled after Start of COVID-19 pandemic.
- Number of participants who terminated the study treatment by main reason (adverse event, lost to follow-up, protocol non-compliance, death, PD, withdrawal by subjects and other).
- Number of participants who terminated the study treatment due to COVID-19.
- Number of participants who discontinued the study and primary reasons for study discontinuation (adverse event, lost to follow-up, protocol non-compliance, death, withdrawal by participants and other).
- Number of participants who discontinued the study due to COVID-19.
- Number and percentage of participants who re-initiated the bintrafusp alfa treatment.
 - Number and percentage of subjects who discontinued treatment after re-initiation.

10.2 Protocol Deviations / Exclusion from Analysis Sets

10.2.1 Important Protocol Deviations

Important protocol deviations (IPDs) are protocol deviations that might significantly affect the completeness, accuracy, and/or reliability of the study data or that might significantly affect a participant's rights, safety, or well-being.

Important protocol deviations include:

- Participants enrolled and dosed on the study who did not satisfy enrolment criteria
- Participants that develop withdrawal criteria while on the study but are not withdrawn
- Participants that receive the wrong study intervention or an incorrect dose
- Participants that receive an excluded concomitant medication
- Failure to collect data necessary to interpret primary endpoints
- Failure to collect necessary key safety data
- Deviation from Good Clinical Practice (GCP)
- Any other protocol deviation that might significantly affect the completeness, accuracy, and/or reliability of the study data or that might significantly affect a participant's rights, safety, or well-being.

Important protocol deviations will be identified for all participants by either site monitoring, medical review processes or programming and confirmed prior to or at the Data Review Meeting at the latest.

Any IPD is documented in SDTM datasets whether identified through site monitoring, medical review or programming. The management of protocol deviations is outside of this IAP document.

Clinically important protocol deviations (CIPDs) are a subset of IPDs that could impact the key objectives of the study and that would lead to the exclusion of a participant from an analysis set (see Section 8.1 Definition of Analysis Sets).

CIPDs may be identified during the course of the study but will not require amendments to this IAP.

A listing of IPDs will be provided based on the FAS.

Protocol deviations attributed to the impact of COVID-19 pandemic will be labeled accordingly. Both important and non-IPDs attributable to the COVID-19 pandemic will be included. A listing including protocol deviation impacted by COVID-19 will be provided.

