10.2.2 Reasons Leading to the Exclusion from an Analysis Set

Not applicable.

11 Demographics and Other Baseline Characteristics

If not stated otherwise, the following analyses will be performed based on the FAS per indication or per parent protocol of the corresponding parent study.

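### Does the SAP's definition of clinically important protocol deviations open the way to dropping treated participants from the safety and survival analyses?

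*SAP*

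**What the plan says.** Four places bear on who is analysed.

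- **SAP 10.2.1** defines clinically important protocol deviations (CIPDs) as a subset of important protocol deviations (IPDs) "that could impact the key objectives of the study and that would lead to the exclusion of a participant from an analysis set", with a pointer to Section 8.1. It adds: "CIPDs may be identified during the course of the study but will not require amendments to this IAP". The IPDs from which CIPDs are drawn include "Participants enrolled and dosed on the study who did not satisfy enrolment criteria". It also states: "The management of protocol deviations is outside of this IAP document".
- **SAP 8.1** defines the FAS and the SAF as in the parent protocol and says that each will "include all participants who receive at least one dose of study intervention in the Rollover study". It closes with: "The final decision to exclude participants from any analysis set will be made during the Data Review Meeting prior to database lock".
- **SAP 10.2.2**, headed "Reasons Leading to the Exclusion from an Analysis Set", has a single entry saying that the item does not apply.
- **Protocol 9.3** takes both sets from the parent protocols and, like SAP 8.1, leaves any final exclusion to a data review meeting before lock.

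The SAF carries the primary adverse event analysis, the FAS carries overall survival, and the Enrolled Analysis Set is used for disposition only. There is no per-protocol set.

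**The concern.** Section 10.2.1 ties a class of deviation to exclusion and allows members of that class to be identified later without amending the SAP. Section 8.1 then gives a meeting the last word on exclusions. Yet the section meant to list the reasons lists none, and the cross-reference from 10.2.1 to 8.1 leads to no deviation criterion.

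With no per-protocol set, a CIPD exclusion could affect results only by taking someone out of the SAF or the FAS. Someone enrolled in breach of the eligibility criteria and then dosed has still been exposed to the drug, so removal from the SAF would discard genuine safety information. The study is open-label, so adverse events and deaths could be known when membership is settled. In a study this small, one removal could visibly change a percentage, and an event seen only in that participant would disappear from the table. At stake would be an outcome-aware choice of denominator for the primary endpoint.

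**Working it through.** The plan states no figure to reproduce. The check is a comparison of the texts, followed by a bound on what one exclusion could do.

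**Step 1: is there an exclusion rule that an analyst could apply?** Such a rule needs a trigger, an affected set and a stated reason.

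| Element | Where it would be | What is there |
|---|---|---|
| Trigger: a named CIPD | SAP 10.2.1 | A definition; no deviation is named as a CIPD |
| Affected set | SAP 8.1 | Every participant with a rollover dose is in the FAS and SAF, subject to the parent definitions; no deviation criterion |
| Reason | SAP 10.2.2 | Marked as not applicable |
| Decision maker | SAP 8.1, protocol 9.3 | Data Review Meeting before lock |

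Only the decision maker is filled in. The CIPD clause says what such a deviation would be. It does not say that any exists, or from which set a participant would be taken. Section 10.2.2 answers the reasons question by saying that it does not arise. An analyst programming from these sections would flag as FAS and SAF everyone with a rollover dose who meets the parent definition, and would program no deviation-based removal.

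**Step 2: does anything depend on the denominator?** Protocol 9.4.2 tabulates the safety endpoints with descriptive statistics, and the study has a single arm. There is no hypothesis test, margin or decision threshold. Overall survival is summarised by Kaplan-Meier quartiles, per group only where at least 5 participants are enrolled (SAP 14.1.1).

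**Step 3: bound for one exclusion, if it happened anyway.** Let k of n participants have an event, and remove one participant.

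- The removed participant had the event: (k−1)/(n−1) − k/n = −(n−k)/[n(n−1)]. This is largest in size at k = 1, giving −1/n.
- The removed participant did not: k/(n−1) − k/n = k/[n(n−1)]. This is largest at k = n−1, giving +1/n.

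Input: n = 10, the estimated minimum for the whole study in the protocol synopsis.

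- k = 1, event in the removed participant: 1/10 = 10.0% becomes 0/9 = 0%, a fall of 10.0 points.
- k = 1, event in another participant: 1/10 = 10.0% becomes 1/9 = 11.1%, a rise of 1.1 points.
- k = 9, no event in the removed participant: 9/10 = 90.0% becomes 9/9 = 100%, a rise of 10.0 points.

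The tables are by indication or parent protocol, so a group may be smaller than the study and its bound of 1/n correspondingly larger. The documents give neither group sizes nor an upper limit on enrolment. The bound holds for any small descriptive study that loses one participant; it is not evidence that this plan loses one.

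**Step 4: would a removal leave a trace?** SAP 10.2.1 keeps every IPD in the SDTM data, and disposition is reported on the Enrolled Analysis Set. Dropping a dosed participant for a deviation would depart from the membership statement in 8.1. Protocol 9.4 requires major modifications of planned analyses to be reflected in an amendment or in the clinical study report.

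**The case for a change.** The best case for acting is that discretion without criteria is what a SAP should avoid, and that closing the gap costs a few sentences. The meeting can exclude from any set, CIPDs can be named late, and outcomes are visible. Disclosure also has a weak spot: "A listing of IPDs will be provided based on the FAS", so a participant removed from the FAS would drop out of that listing too.

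Part of this stands. Sections 10.2.1 and 10.2.2 do not fit together, and the pointer to 8.1 finds no criterion.

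The rest is weaker than it looks:

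- Discretion to exclude is not a planned exclusion. SAP 8.1 and protocol 9.3 agree on the meeting's role, and restricting that role would create a departure from the protocol that does not exist today.
- It cannot be said that no criteria exist. Deviation management is placed outside the SAP, the set definitions rest partly on parent protocols that are not in hand, and SAP Section 9 is redacted.
- The rule in protocol 9.4.2 about analysing participants by actual treatment does not settle the matter. It says which treatment a participant is counted under, not who belongs to the SAF.
- The documents place the meeting before lock without saying how close to it, so how much outcome data would be known is uncertain.

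**Conclusion.** The inconsistency is real but clerical. The CIPD clause defines a category that the rest of the SAP leaves empty, and the sensible reading, which 8.1 and 10.2.2 support, is that no participant with a rollover dose is removed from the SAF or FAS for a protocol deviation. On that reading the planned analysis is the same whether or not the clause is tidied: same participants, same denominators, same tables. The effect on results is therefore nil. The 10-point figure at n = 10 describes only an exclusion that the visible text does not plan, in an analysis with no inferential decision attached. No change is called for.

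This rests on two assumptions: that the parent-protocol definitions of the FAS and SAF contain no deviation-based removal, and that the redacted SAP text adds none. Neither can be checked from the documents supplied.
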